## 6.1 Subject Disposition, Completion Rate and Reasons for Discontinuation

Subject disposition will be summarized for the Enrolled Sample by parent study treatment group for rollover subjects, de novo subjects and overall.

Subject completion rate and reasons for discontinuation will be summarized for the Enrolled Sample by parent study treatment group for rollover subjects, de novo subjects and overall.

## 6.2 Treatment Compliance

For each subject, compliance in taking IMP is calculated by dividing the number of tablets taken by the total number of tablets the patients were scheduled to take during the study period. Compliance is calculated on the IMP for the study period. For lost-to-follow up patients, the last IMP end date record will be used as the treatment end date.

## 6.3 **Protocol Deviation**

Protocol deviations are summarized by center and type of deviation for enrolled subjects by parent treatment group. Listing of protocol deviation will list the treatment phases during which the deviations occurred.

# 7 Baseline Characteristics

## 7.1 Baseline Definition

Baseline is defined as the last available measurement prior to the first dose of open-label IMP in the open-label treatment period.

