1.3 Known and Potential Risks and Benefits

Based on the IB, data from the completed phase 1 and 2 trials indicate that centanafadine is safe and well-tolerated in healthy adult subjects and adult subjects with ADHD. Data from the completed phase 2 trials demonstrate that centanafadine is effective in treating symptoms of ADHD; based on the positive effect of centanafadine SR on the primary efficacy measure, the adult ADHD-RS-IV. Centanafadine may also confer an improved safety profile and lower potential for abuse compared to currently approved Schedule II stimulant treatments for ADHD. The abuse potential for centanafadine is continuing to be evaluated.

Seven clinical trials in 260 subjects and subjects with ADHD have been conducted with centanafadine. A total of 140 healthy subjects received centanafadine in 5 phase 1 trials and 120 subjects with ADHD received centanafadine in 2 phase 2 trials. The most common AEs reported in trials with centanafadine SR at TDDs ranging from 25 to 800 mg were gastrointestinal (nausea, diarrhea, and dry mouth), metabolism/nutrition-related (decreased appetite), and nervous system disorders (headache, dizziness, and insomnia). In general, these AEs were mild and resolved.

Confidential - Proprietary Information

22

To date, 1 serious AE (SAE) (ischemic cardiovascular accident) occurred in a subject with ADHD (initial dosage of centanafadine SR 100 mg, titrated to 500 mg) 6 days after completing treatment, but it was not considered related to centanafadine treatment.

Based on the outcome of the phase 2 trials, treatment with centanafadine may be associated with increases in blood pressure, heart rate and orthostatic blood pressure changes. Increases in blood pressure and heart rate were usually modest and asymptomatic; however, hypertension, tachycardia, and orthostasis have occurred. During clinical trials, heart rate and blood pressure will be measured prior to initiation of therapy, and periodically while on therapy. Subjects will also be monitored for tachycardia or hypertension. Centanafadine should be used with caution in subjects with hypertension, tachycardia, or cerebrovascular disease or cardiovascular disease (eg, known serious structural cardiac abnormalities, cardiomyopathy, serious heart rhythm abnormalities, or other serious cardiac problems that may place a subject at increased vulnerability to noradrenergic effects).

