3.3.2 Subject Selection and Numbering

At screening, only de novo subjects will be assigned a unique subject ID number upon signing the electronic informed consent form (eICF) based on sequential enrollment in the trial. The clinical site will maintain a list identifying all subjects by their subject ID number and initials. Subjects that rollover from Trials 405-201-00013 or 405-201-00014 will retain their subject ID number from the prior trial upon entry in to Trial 405-201-00015.

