4.1 Prohibited Medications

Rollover subjects who enrolled from Trial 405-201-00013 or Trial 405-201-00014 will washout from centanafadine for at least one week before the baseline visit of the open-label trial. Rollover subjects who are willing to enroll in this trial must not start any new medication for ADHD after the Week 6 visit in Trial 405-201-00013 or Trial 405-201-00014.

De novo subjects who are currently taking any medication for adult ADHD at screening will washout from their current ADHD medication before the baseline (Day -1) visit. De novo subjects must agree to discontinue all prohibited medications during the screening period. Table 4.1-1 provides the required duration of washout for selected prohibited medications. All other prohibited medications must be discontinued at least 24 hours before the first dose of IMP.

| Table 4.1-1Washout of Prohibited Medications Required Before the Trial - De Novo Subjects | | |
|--|--|----------------------------------|
| | Medication | Required Washout Prior to Dosing |
| 1. | Antidepressants | |
| | Fluoxetine | 28 days |
| | All other antidepressants | 14 days |
| 2. | Benzodiazepines | 7 days |
| 3. | Hypnotics, including non-benzodiazepine sleep aids | 7 days |
| 4. | ADHD medications | |
| | Stimulants | 7 days |
| | Nonstimulants | 21 days |
| 5. | Sedating antihistamines (eg, diphenhydramine, | 7 days |
| | hydroxyzine, chlorpheniramine), unless meeting | |
| | critieria in Table 4.1-2 (1. [j]) | |
| 7. | Antihypertensives | 21 days |
| | Clonidine | |
| | Propranolol | |
| | Guanfacine | |
| 8. | Anorexics (weight loss supplements) | 7 days |

Confidential - Proprietary Information

Table 4.1-2 lists all medications prohibited during the trial, including exceptions, where appropriate. Prohibited medications may be considered for a documented and clinically appropriate indication (eg, episodic pain condition, tooth extraction) in short-term basis and must not be prescribed as a treatment for a chronic disease.

| Table 4.1-2List of Medications Prohibited During the Trial | | |
|--|---|--|
| 1. | All psychotropic agents including, but not limited to, the following: a) Antipsychotics, including depot formulations b) Anticonvulsants c) Antidepressants d) Mood stabilizers (ie, lithium) | |

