# Rollover Subjects from Double-blind Phase 3 Trial (i.e., Trial 405-201-00013 or Trial 405-201-00014)

*Open-label Screening/Baseline:* Subjects who completed one of the double-blind phase 3 trials may be eligible to enroll in this trial; subjects who discontinued will not be eligible. Subjects who complete both the 6-week double-blind treatment period and the 7-day follow-up visit are eligible to enroll into this trial. Subjects will be evaluated for eligibility at the 7-day follow-up visit of the double-blind phase 3 trial, and informed consent will be obtained before any procedures for the open-label trial are conducted. Therefore the assessments from the 7-day follow-up visit of the double-blind phase 3 trial may serve as the baseline assessments for the open-label trial.

*Open-label Treatment:* Eligible subjects from the double-blind phase 3 trial will receive daily treatment with open-label centanafadine SR tablets as described in Section 3.2 of the protocol.

During the open-label treatment period, subjects will return to the clinic for evaluations at the end of Weeks 1, 2, 4, 8, 12, 16, 20, 26, 32, 38, 44, and 52/ET. A Week 48 visit will be conducted via telephone, web, or other acceptable means of contact.

*Follow-up:* If any subject discontinues the trial early, every effort should be made to complete the early termination (ET) evaluations as soon as possible and, whenever possible, prior to starting any new medication or treatment. All subjects (completers and early withdrawals) will be evaluated for safety during a 10-day follow up (follow-up telephone calls at 1, 3, and 5 days after the last dose of IMP, in-clinic visits 2 and 7 days after the last dose of IMP, and a follow-up telephone call [or web, or other acceptable means of contact] 10 days after the last dose of IMP).

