## 9.3 Physical Examination and Vital Signs

Summary statistics for changes from baseline in vital signs will be provided for the Safety Sample. By-patient listings will be provided for physical examination.

Potentially clinically relevant vital signs measurements identified in the open-label treatment phase for the Safety Sample will be listed and summarized. Criteria for identifying vital signs of potential clinical relevance are provided in Appendix 1.

In addition, the change from baseline in weight, BMI, and waist circumference, and potentially clinically relevant abnormalities in weight, will also be summarized.

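### For rollovers who took centanafadine in the parent trial, the only baseline in SAP 7.1 is not a pre-centanafadine value, so long-term change in weight and other slow measures may be misstated.

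*SAP*

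**What the plan says.** SAP 7.1 has a single rule for all subjects: "Baseline is defined as the last available measurement prior to the first dose of open-label IMP in the open-label treatment period". SAP 8 repeats it for efficacy, and Protocol 7.4.3 and 7.6 agree.

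For rollovers, SAP 3 fixes what comes before that point: "Subjects who complete both the 6-week double-blind treatment period and the 7-day follow-up visit are eligible to enroll into this trial". It adds that "the assessments from the 7-day follow-up visit of the double-blind phase 3 trial may serve as the baseline assessments" for the open-label trial. Under Protocol 3.7.1.1.1 the physical examination and blood samples are taken at that same visit. Protocol 4.1 states that rollovers "will washout from centanafadine for at least one week before the baseline visit of the open-label trial".

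SAP 9.3 summarises "change from baseline in weight, BMI, and waist circumference". SAP 9.2 does the same for HbA1c and routine laboratory values, which include lipids (Protocol Table 3.7.4.2-1). SAP Appendix 1 flags a weight change of 7% or more in either direction, judged only against baseline.

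SAP 8 and 9 present results by parent treatment group, for de novo subjects, and overall. SAP 6 counts late rollovers as de novo. Neither document defines a change from the value before the first parent-trial dose.

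**The concern.** The trial's purpose is long-term safety, and Protocol 1.3 names decreased appetite among the most common adverse events, so weight is a foreseeable slow variable. A subject from an active parent arm can receive 6 + 52 = 58 weeks of centanafadine over the two trials, but the change tables start after the first 6 weeks and a gap of about a week. Weight, BMI, waist, HbA1c and lipids need not return to their pre-drug level in that gap. Whatever has not returned is built into the reference value.

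Three summaries are exposed. The mean changes for these subjects may not show the full change since first exposure. The 7% weight flag starts from a shifted point. The overall column pools these subjects with others whose baseline precedes any centanafadine. The group with the longest total exposure is the one for which cumulative change is least visible.

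**Working it through.** The sample size is not power-based and no planned figure depends on the baseline rule, so there is nothing to reproduce. The check is a reading of the timeline plus simple arithmetic.

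**Inputs from the documents**
- Rollovers about 560, de novo about 145 (SAP 4, Protocol 7.1). Sum 560 + 145 = 705, close to the approximate total of 720 in Protocol 3.3.1.
- Time before rollover baseline: 6 weeks double-blind, then at least one week off centanafadine (SAP 3, Protocol 4.1).
- Weight flag: change of at least 7%, up or down, with no absolute criterion (SAP Appendix 1).

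**Assumptions, because the documents give no figure**
- Share s of rollovers who had centanafadine in the parent trial: 1/3, 1/2, 2/3.
- Fraction w of pre-drug weight already lost at the open-label baseline: 0%, 1%, 2%, 3%.

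**Step 1. Subjects affected** = s × 560, and as a share of 705.
- s = 1/3: 187 (27%)
- s = 1/2: 280 (40%)
- s = 2/3: 373 (53%)

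The number of late rollovers is not given, so they are not counted separately here.

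**Step 2. Weight flag.** With pre-drug weight set to 1, baseline weight is b = 1 − w.
- A true 7% loss from pre-drug shows as 1 − 0.93/b.
- The decrease flag needs a loss from pre-drug of 1 − 0.93b.
- The increase flag needs a gain from pre-drug of 1.07b − 1.

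| w | True 7% loss shows as | Loss needed to flag | Gain needed to flag |
|---|---|---|---|
| 0% | 7.0% | 7.0% | 7.0% |
| 1% | 6.1% | 7.9% | 5.9% |
| 2% | 5.1% | 8.9% | 4.9% |
| 3% | 4.1% | 9.8% | 3.8% |

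At w = 1%, for example, 1 − 0.93/0.99 = 6.1%. With any carried-over loss, a true 7% loss is not flagged, while a gain of less than 7% over the pre-drug weight can be.

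**Step 3. Overall column.** The shift in overall mean change is roughly s × (560/705) × w, assuming the same w in every affected subject and equal retention. At the smallest non-zero case, 1/3 × 0.794 × 1% = 0.26 percentage points. At the largest, 2/3 × 0.794 × 3% = 1.59 percentage points. At w = 0 it is zero.

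**Step 4. Which measures are exposed.** The weight flag is purely relative, so it is fully exposed. For lipids the flags in SAP Appendix 2 are absolute thresholds, so only the mean changes are exposed. Mean changes in BMI, waist and HbA1c are exposed in the same way.

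**The case against.** The strongest case for leaving the plan alone is that the SAP follows the protocol's own prespecified baseline, and change from the start of open-label dosing is a natural question for a 52-week treatment period. Change since first exposure is a cross-trial question that an integrated analysis may answer; the documents do not say. Results are split by parent arm, and baseline weight and BMI are too (SAP 7.2), so a sizeable average carry-over could be seen. Nor would a parent-trial baseline be a clean untreated one: rollovers were washed out of other drugs before that trial, and de novo subjects may stop stimulants only 7 days before baseline.

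Much of this stands. The planned tables are legitimate and should remain. The remedy gives a pre-centanafadine reference, not a treatment-free one. But the parent-arm columns identify the affected group without changing its reference value. They cannot correct an individual's 7% flag or the overall column. They also miss late rollovers, who may have had centanafadine but sit in the de novo column.

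A reader might infer that these subjects are still on treatment at baseline. They are not: Protocol 4.1 requires at least a week off. A reader might also infer that long-term change is shown to be understated. The documents contain no data on carry-over at day 7, so neither its size nor its presence is established. For AISRS, residual benefit and withdrawal effects would push in opposite directions. For blood pressure and heart rate the documents offer no argument that an effect persists after a week.

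**Conclusion.** The point holds as a gap in the additional safety summaries. For parent-centanafadine rollovers the sole baseline is off drug but not pre-centanafadine, and nothing in either document supplies the missing reference.

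About 27% to 53% of the planned 705 subjects are affected if one third to two thirds of rollovers had active drug. The effect on weight runs from none at zero carry-over to a true 7% loss appearing as 4.1% at 3% carry-over. Both ranges are assumptions. The direction (losses understated, gains overstated) assumes that the carried-over effect is weight loss; the documents give no direction for HbA1c or lipids. For late rollovers the time off drug is not stated and the parent treatment may have been cut short, so their carry-over is less certain still.

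It would be wrong to conclude that the primary result is compromised. The primary endpoint is the frequency and severity of treatment-emergent adverse events, which does not use a change from baseline in these measures.

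**What to change.** Keep all current tables. Add to SAP 7.1 a supplementary pre-centanafadine baseline:

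- For rollovers who received centanafadine in Trial 405-201-00013 or 405-201-00014, including late rollovers analysed as de novo, use the last value before the first double-blind dose, where the parent trial collected the measure.
- Rollovers from a parent arm without centanafadine, and true de novo subjects, keep the open-label baseline.
- From this baseline, present change in weight, BMI, waist, HbA1c and lipids, and the two-sided 7% weight flag, beside the existing tables.
- AISRS is optional. Blood pressure and heart rate are not needed.

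The cost is SAP wording, a data merge and a few extra tables, with no change to trial conduct. The merge is straightforward for ordinary rollovers, who "will retain their subject ID number from the prior trial" (Protocol 3.3.2). Late rollovers follow the de novo path and the documents do not say which ID they carry, so that link should be confirmed. The documents also do not show which measures the parent trials collected before dosing; the SAP should list those available.

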## 7.2 Demographic Characteristics

Baseline demographic characteristics including age, race, ethnicity, gender, weight, height, and body mass index (BMI) will be summarized by descriptive statistics (frequency, mean, median, standard deviation, maximum, minimum, and percentage when applicable) for the Enrolled Sample by parent study treatment group for rollover subjects, de novo subjects and overall.

#### 7.3 Medical and Psychiatric History

A summary of medical and psychiatric history will be presented for the Enrolled Sample by parent study treatment group for rollover subjects, de novo subjects and overall.

A summary of the Adult ADHD Clinical Diagnostic Scale (ACDS) at screening will also be presented for the Enrolled Sample (by parent study treatment group for rollover subjects, de novo subjects and overall). The number and percentage of patients with each response to items A23-A41 from Section A (Childhood ADHD Symptoms Summary), B22-B39 from Section B (Adult ADHD Symptoms Summary), and C1-C5 will be presented.

#### 7.4 Baseline Psychiatric Evaluation

Baseline psychiatric scale evaluation for the open-label treatment period will be summarized for the Enrolled Sample by parent study treatment group for rollover subjects, de novo subjects and overall. The mean, median, range and standard deviation will be used to summarize the assessments of: AISRS total score, CGI - Severity of Illness Score (CGI-S), and ADHD Impact Module – Adult (AIM-A).

## 8 Efficacy Analysis

Exploratory (efficacy) endpoints for the open-label trial are:

- Change from baseline in AISRS Total Score, by trial visit and at the last visit (i.e., Week 52/ET);
- Change from baseline in CGI-S, by trial visit and at the last visit (i.e., Week 52/ET);
- Change from baseline in AIM-A Score by trial visit and at the last visit;

CCI

Descriptive statistics will be provided for each endpoint and will be summarized at each trial visit based on the Efficacy Sample using the OC dataset and at the last visit using the LOCF dataset. These summaries will be presented by parent study treatment group for rollover subjects, de novo subjects and overall. Baseline is defined as the last available measurement prior to the first dose of open-label IMP in the open-label treatment period.

For AIM-A, the following will be provided:

 Change from baseline for Question 1 (Global Quality of Life) and Questions 9Aa – 9Ai and 9Ba – 9Bi (Impact of Symptoms) of AIM-A at scheduled visits during the open-label treatment period, separately at every visit

- 2) Proportion of subjects in each response for the following questions of AIM-A at scheduled visits during the open-label treatment period, separately at every visit
  - a. Questions 2-4 (Global Quality of Life)
  - b. Questions 5a-5j (Living with ADHD)
  - c. Questions 6a-6k (General Well-Being)
  - d. Questions 7a-7j (Work, Home and School Performance and Daily Functioning)
  - e. Questions 8a-8h (Relationships and Communication)
  - f. Economic impact (5 items)
  - g. Questions 17-23 (Demographics/Medication Status)

The key outcome measures from the CANTAB assessments include the following:

Confidential - Proprietary Information1315 September 2021Until the information herein is released by Otsuka to the public domain, the contents of this document are Otsuka
confidential information and should not be duplicated or re-distributed without prior written consent of Otsuka.

#### 8.1 COVID-19 Related Supplementary Analyses

Summary statistics for mean and mean change from baseline in AISRS Total Score, by trial visit and at the last visit (i.e., Week 52/ET) and by visit type (face-to-face vs. virtual) based on the Efficacy Sample will be provided by parent study treatment group for rollover subjects, de novo subjects and overall.

## 9 Safety Analysis

The primary safety endpoint analysis is the frequency and severity of AEs in the open-label treatment period (see Section 9.1). Other standard safety variables to be analyzed include clinical laboratory tests, vital signs, body weight, waist circumference, BMI, 12-lead electrocardiograms (ECGs), and physical examinations. In addition, data from the following safety scales will be evaluated: C-SSRS and Study Medication Withdrawal Questionnaire (SMWQ).

Safety analyses will be conducted based on the Safety Sample, and summary statistics will be provided by parent study treatment group for rollover subjects, de novo subjects and overall, unless otherwise indicated.

Unless otherwise specified, in general, analysis of safety data will be performed on observed case and for last visit.

#### 9.1 Adverse Events

All adverse events will be coded by System Organ Class (SOC) and Preferred Term (PT) according to the Medical Dictionary for Regulatory Activities (MedDRA). AEs that are sexspecific, e.g., ovarian cancer, will have their incidence rates evaluated for the specific sex.

Treatment-emergent AEs (TEAEs) are defined as AEs with an onset date on or after the first dose of IMP. In more detail, TEAEs are all adverse events which started after start of IMP; or if the event was continuous from baseline and was worsening, serious, study drug related, or resulted in death, discontinuation, interruption or reduction of study therapy. Adverse events occurring up to 30 days after the last day of IMP will be included in the summary tables.

The incidence of the following events in the open-label treatment phase will be summarized using the Safety Sample:

- a) Treatment-emergent AEs (TEAEs)
- b) TEAEs by severity
- c) TEAEs potentially causally related to the IMP
- d) TEAEs with an outcome of death
- e) Serious TEAEs
- f) TEAEs leading to discontinuation of the IMP
- g) Treatment-emergent Adverse Events of Special Interest (AESI)
- h) Abuse-related TEAEs and TEAEs involving MHIs (Medication handling irregularities)

AEs will be classified by Primary SOC and PT according to the MedDRA. AEs that are gender-specific, e.g., ovarian cancer, will have their incidence rates evaluated for the specific gender.

Incidence of TEAEs will be summarized for the open-label treatment period. Incidence of TEAEs by SOC and MedDRA PT will be summarized for sex and race.

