| | Baseline | Baseline 52-Week Open-label Treatment Period | | | | | | | | | | |
| | 7-day follow-up visit from Trial 405-201-00013 or | W 1 & | | | | | | | | End of Treatment | | |
| | Trial 405-201-00014/ | 2 | W 4, 8, 12 & | W 20 | W 26 | W 32 | W 38 | W 44 | W 48 ^b | | | |
| | Baseline for | (± 3 | 16 | (± 3 | (± 3 | (± 3 | (± 3 | (± 3 | (± 3 | W 52/ET | | |
| | Trial 405-201-00015 ^a | days) | (± 3 days) | days) | days) | days) | days) | days) | days) | (± 3 days) | | |
| Visit | 1 | 2 & 3 | 4, 5, 6, & 7 | 8 | 9 | 10 | 11 | 12 | 13 | 14 | | |
| OTHER | | | | | | | | | | | | |
| IMP dispensing | Х | Х | Х | Х | Х | Х | Х | Х | | | | |
| IMP return and accountability | | Х | Х | Х | Х | X | Х | Х | | Х | | |

AIM-A = ADHD Impact Module – Adult; AISRS = Adult ADHD Investigator Rating Scale; C-SSRS = Columbia-Suicide Severity Rating Scale; ECG=electrocardiogram; PT/INR = prothrombin time/international normalized ratio; W = week.

^aDosing will commence the day after the baseline visit.

^bTelephone, web, or other acceptable means of contact.

^cAssessments may be conducted at the 7-day follow-up visits of Trial 405-201-00013 or Trial 405-201-00014, and the information can be carried over into Trial 405-201-00015 for the baseline visit.

^dIf the urine pregnancy test is positive, the result will be confirmed with a serum pregnancy test.

^ePhysical examination at baseline will include height measurements.

^fWeek 8 only.

^gWeeks, 4, 8, and 16 only.

^hWeeks 4 and 12 only.

¹Alcohol testing may be conducted via a blood test or using a breathalyzer.

CCI CCI

Confidential - Proprietary Information

| Table 3.7-2Schedule of Assessments - RFollow-up | ollover Subjects from | n Trial 40: | 5-201-00013 | 3 or Trial 4 | 05-201-00014 | - |
|---|--|--|---|---|---|--|
| Period | | | Follow- | up ^a | | |
| | 1 (+1) days after the last dose of IMP | 2 (+1) days after the last dose of IMP | 3 (+ 1) days after the last dose of IMP | 5 (+ 1) days after the last dose of IMP | 7 (+ 2) days after the last dose of IMP | 10 (+ 2) days after the last dose of IMP |
| Visit | 15 | 16 | 17 | 18 | 19 | 20 |
| ENTRANCE/HISTORY | | | | | | |
| Concomitant medication(s) | Х | Х | Х | Х | Х | Х |
| EFFICACY | | | | | | |
| AISRS | | Х | | | Х | |
| SAFETY | | | | | | |
| Adverse events | Х | Х | Х | Х | Х | Х |
| Vital signs | | Х | | | Х | |
| SMWQ | Х | Х | Х | Х | Х | Х |
| Urine drug screen | | Х | | | Х | |
| Alcohol testing ^b | | Х | | | X | |
| C-SSRS | | X | | | Х | |

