3.7.1.3 Follow-up Period

All subjects, whether they complete the trial or are withdrawn prematurely for any reason, will be followed up for a safety evaluation during a 10-day follow up period (follow-up telephone calls at 1, 3, and 5 days after the last dose of IMP, in-clinic visits 2 and 7 days after the last dose of IMP, and a follow-up telephone call [or web, or other acceptable means of contact] 10 days after the last dose of IMP).

The following procedures will be performed at the 1-day, 3-day, and 5-day follow-up visit:

- The SMWQ questionnaire will be completed remotely.
- AEs will be recorded.
- Concomitant medications will be recorded.

The following procedures will be performed at the 2-day and 7-day follow-up visit:

Confidential - Proprietary Information

58

- A qualified rater will administer the AISRS.
- The SMWQ questionnaire will be completed in-clinic.
- Vital sign measurements will be recorded.
- Alcohol testing may be conducted via a blood test or using a breathalyzer.
- Urine will be collected for urine screen(s) for drugs of abuse.
- The investigator (or qualified designee) will complete the "Since Last Visit" C-SSRS form.
- AEs and concomitant medications will be recorded.

The following procedures will be performed at 10-day follow-up contact:

- The SMWQ questionnaire will be completed remotely.
- AEs and concomitant medications will be recorded.

Depending upon the type of follow-up required, other evaluations or tests may be conducted or performed.

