5.9.2 Follow-up of Serious Adverse Events and Immediately Reportable Events

This trial requires that subjects be actively monitored for SAEs and IREs up to 10 days after the last dose of IMP is administered.

Serious AEs and nonserious IREs that are **identified or ongoing at the last scheduled contact** must be recorded as such on the AE eCRF page. If updated information (eg, resolved status) on SAE or IRE status becomes available after a subject's last scheduled contact (up to last in-clinic visit for the entire trial), this must be reported to the sponsor according to the appropriate reporting procedures. The investigator will follow SAEs until the events are resolved, stabilized, or the subject is lost to follow-up or has died. Resolution means that the subject has returned to the baseline state of health and stabilized means that the investigator does not expect any further improvement or worsening of the subject's condition. The investigator will continue to report any significant follow-up information to the sponsor up to the point the event has resolved or stabilized, or the subject is lost to follow-up, or has died.

Confidential - Proprietary Information

81

5.9.3 Follow-up and Reporting of Serious Adverse Events and Immediately Reportable Events Occurring after Last Scheduled Contact

Any new SAEs or IREs reported to the investigator which occur **after the last scheduled contact** and are determined by the investigator to be reasonably associated with the use of the IMP, should be reported to the sponsor. This may include SAEs or IREs that are captured on follow-up telephone contact or at any other time point after the defined trial period. The investigator should follow SAEs or IREs identified after the defined trial period and continue to report any significant follow-up information to the sponsor until the events are resolved or stabilized, or the subject is lost to follow-up or has died.

6 Pharmacokinetic/Pharmacogenomic Analysis

No PK or pharmacogenomic analysis is planned.

7 Statistical Analysis

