7.4 Primary, Secondary, and Exploratory Endpoint Analyses

7.4.1 Primary Endpoint Analysis

The primary (safety) endpoint analysis is the frequency and severity of AEs (including evaluations of rash and abuse potential) in the open-label treatment period. All AEs will be coded using the MedDRA PTs. The incidence of TEAEs will include the following summaries:

- TEAEs
- TEAEs by severity
- TEAEs potentially causally related to the IMP
- TEAEs with an outcome of death
- Serious TEAEs
- TEAEs leading to discontinuation of the IMP
- Abuse-related AEs and AEs involving medication handling irregularities

A TEAE is defined as an AE that starts after the first dose of IMP or an AE that is reported at baseline and increases in intensity or becomes serious or trial drug-related or results in death, discontinuation, interruption, or reduction of IMP.

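### SAP 9.1 counts adverse events to 30 days after the last dose, but scheduled AE collection stops at the 10 (+2)-day contact, so later events enter the treatment-phase tables only selectively

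*SAP*

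**What the plan says.** **SAP.** Section 9 makes AEs the primary analysis and ties them to treatment: "The primary safety endpoint analysis is the frequency and severity of AEs in the open-label treatment period". Section 9.1 introduces the TEAE tables with "The incidence of the following events in the open-label treatment phase will be summarized using the Safety Sample", and the same section carries the 30-day rule: "Adverse events occurring up to 30 days after the last day of IMP will be included in the summary tables". The table list in SAP 12 has no separate table for AEs with onset after treatment.

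**Protocol, primary analysis.** Section 7.4.1 names the same period: "The primary (safety) endpoint analysis is the frequency and severity of AEs (including evaluations of rash and abuse potential) in the open-label treatment period". Its TEAE definition gives a start (after the first dose) but no end date.

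**Protocol, collection.** Tables 3.7-2 and 3.7-4 and Section 3.7.1.3 record AEs of all kinds at follow-up Days 1, 2, 3, 5, 7 and 10. The last column is headed "10 (+ 2) days after the last dose of IMP". Section 5.9.2 sets the term for active monitoring: "This trial requires that subjects be actively monitored for SAEs and IREs up to 10 days after the last dose of IMP is administered". Section 5.9.1 has nonserious, non-IRE events still open at the last contact simply marked as ongoing. For new events after that contact, Section 5.9.3 asks for SAEs or IREs that come to the investigator's notice and "are determined by the investigator to be reasonably associated with the use of the IMP". Section 5.1 defines IREs as SAEs, AEs of special interest (skin eruptions), occupational-exposure AEs, potential serious hepatotoxicity and pregnancy.

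**The concern.** The analysis window is longer than the collection window. Up to the last follow-up contact, every kind of AE is asked about. Beyond it, an event reaches the sponsor essentially only if it is serious or otherwise reportable and also judged drug-related. Placing both in one numerator mixes full ascertainment with filtered ascertainment, and the filter uses the same attributes (seriousness, relatedness, special interest) that several of the tables report.

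The result is neither on-treatment incidence, which the table label promises, nor complete 30-day post-dose incidence, which the cut-off suggests. These tables carry the trial's primary endpoint, and a reader of the report could not tell which events came from which period.

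**Working it through.** No sample-size, alpha or power figure depends on this point, since Protocol 7.1 does not base the sample size on power. There is therefore no plan figure to reproduce. The check compares the two windows.

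**Inputs**
- End of the summary window: Day 30 after the last dose (SAP 9.1).
- Last scheduled AE contact: Day 10, or Day 12 with the +2 allowance (Protocol Tables 3.7-2 and 3.7-4).
- Nominal treatment: 52 × 7 = 364 days. Half of it: 26 × 7 = 182 days. A stop at Day 30 is added as an illustrative early withdrawal.

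**Days without scheduled collection** = 30 − day of last contact
- Contact on Day 10: 30 − 10 = 20 days; 20/30 = 67% of the post-dose window.
- Contact on Day 12: 30 − 12 = 18 days; 18/30 = 60%.
- Protocol 3.7.1.2.9 gives the end of follow-up as 10 days after the last dose but also labels it as 14 days after Week 52/ET. If 14 applied, the gap would be 16 days (16/30 = 53%). That label needs reconciling, but a gap remains on any reading.

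**Gap as a share of a subject's summary period** = gap / (treatment days + 30)

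| Treatment days | 20-day gap | 18-day gap |
|---|---|---|
| 364 | 20/394 = 5.1% | 18/394 = 4.6% |
| 182 | 20/212 = 9.4% | 18/212 = 8.5% |
| 30 | 20/60 = 33% | 18/60 = 30% |

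The gap is small for a completer and largest for an early withdrawal. These are shares of time, not of events; the documents give no basis for an event count.

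**What can enter during the gap, and where**
- A new SAE judged associated with the drug: tables CT-8.5.1 (serious), CT-8.3.1 (potentially drug-related) and CT-8.2.9 (both).
- A new skin eruption judged associated: CT-8.3.1 and CT-8.7.1 (special interest), because an AE of special interest is an IRE.
- An ordinary nonserious AE, or an SAE judged unrelated: no route under 5.9.3.
- Exceptions: pregnancy is notified to 30 days in female subjects without the 5.9.3 causality filter (Protocol 5.7), but it goes on the AE form only if there is an abnormality or complication (5.1). A late ET visit may also record any AE volunteered there.

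**Consistency within the SAP.** Section 10.1, which governs the efficacy and safety scales, excludes evaluations more than three days after the last dose, and all follow-up evaluations, from open-label analyses. The AE tables use the same period label with a 30-day tail.

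**The case against.** The strongest reply is that the SAP narrows the protocol rather than stretching it. A TEAE under Protocol 7.4.1 has no end date, so post-dose AEs are already TEAEs and 30 days is a cap. That is correct, but the cap lies beyond the period in which AEs are collected.

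Second, late capture may be rarer than the rule implies. Section 5.9.3 requires reporting to the sponsor, and Protocol 5.3 says the IRE form is not the AE case report form, so late events may not all reach the analysis database. This stands. It makes the count smaller and the capture less even.

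Third, a genuine drug-related SAE on Day 15 is a real event, and incomplete capture understates true 30-day incidence. This also stands, so a blanket claim of inflation would be wrong. What changes is the mix of events, with serious and related ones favoured over ordinary ones.

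Three stronger readings are tempting, and the documents do not support them:
- **That the primary tables must stop at the last dose.** Events from Day 1 to the 10 (+2)-day contact are collected at six contacts and have no capture defect. The one SAE reported in Protocol 1.3 occurred 6 days after treatment ended; a last-dose cut-off as the only definition would take such an event out of the headline serious table.
- **That withdrawal AEs were meant to be studied separately.** Withdrawal is assessed by the SMWQ (Protocol 3.7.4.6.1, SAP 9.6), and the AE window leaves that analysis untouched.
- **That the tail adds about 18% of drug-free time.** That figure takes 300 of 720 at Week 26 and 100 at Week 52 as exact retention, giving a mean exposure of about 167 days and 30/167 = 18%. Protocol 3.3.1 states these as minimum expectations, and no retention curve is given. For a completer the tail is 30/364 = 8% of exposure. In any case, drug-free days do not measure distortion when little is collected in them.

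**Conclusion.** The mismatch is real and modest. For 18 to 20 of the 30 post-dose days, the TEAE tables draw on events filtered by type and attribution while carrying a treatment-phase label. The filter can add to the serious, related and special-interest rows and hardly to ordinary AEs.

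The number of events is probably small, though the documents do not allow it to be estimated. There is no randomised comparison or test, so no alpha or power is affected. The conclusion rests on the follow-up schedule and Section 5.9.3 being applied as written. If the sponsor in practice collects all AEs to Day 30, the gap closes, but the documents should then say so. This is a cheap clarification of the primary tables and does not show the safety conclusions to be unreliable.

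**What to change.** In SAP 9.1:
1. End the TEAE summary tables at the last scheduled AE contact, 10 (+2) days after the last dose, in place of Day 30.
2. Show TEAEs split by onset: first through last dose, and after the last dose through that contact.
3. List later-reported SAEs and IREs separately, with any other AE recorded with a later onset, so that none is lost.
4. Footnote the tables and listing with the collection rule: all AEs to the last contact; afterwards, only the events that Protocol 5.9.3 and the pregnancy provision require.

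Separately, reconcile the 14-day label in Protocol 3.7.1.2.9 with the 10-day follow-up.

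The cost is SAP wording, one added table and the separate listing. Headline counts may fall slightly, with the removed events shown in the listing. No data collection or clinical management changes.
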